17.2.3.1 Evaluation of the Infection Under Study at the Early Clinical Response Assessment

The formal determination of the response to therapy at the Early Clinical Response assessment (72 to 120 hours after administration of the first dose of test article) will be done programmatically using the investigator's assessment of the subject's symptoms associated with CABP entered into the eCRF. The investigator is not responsible for categorizing subjects as Clinical Success, Failure, or Indeterminate at the Early Clinical Response assessment. The severity of the subject CABP symptoms of cough, sputum production, pleuritic chest pain and dyspnea will be evaluated on a 4-point scale (absent, mild, moderate, or severe) based upon the Community Acquired Bacterial Pneumonia Subject Symptom Severity Guidance Framework for Investigator Assessment (see [Appendix 3](#)). A CABP subject symptom severity assessment should be completed at every scheduled evaluation with the exception of the Final Follow-up assessment (see [Section 17.2.1](#) and [STUDY FLOWCHART](#)). For subjects that have been switched to po test article and discharged from the hospital prior to study Day 6, visits must be conducted on study Days 4 and 5, while a study Day 6 visit is optional.

Clinical Success: at the Early Clinical Response assessment will be defined as survival with improvement of at least 1 level (ie, severe to moderate, moderate to mild, mild to absent) compared to Screening in 2 CABP symptoms (cough, sputum production, pleuritic chest pain and dyspnea) with no worsening by at least 1 level in the other inclusion CABP symptoms. In order for the subject to be considered a Clinical Success, the subject may not meet any criteria for Clinical Failure or Indeterminate Early Clinical Response.

Clinical Failure: defined as meeting any of the following criteria:

- There is no improvement by at least 1 level (ie, severe to moderate, moderate to mild, mild to absent) compared to Screening in 2 CABP symptoms.
- Any of the 4 CABP symptoms is worse (by at least 1 level) compared to Screening.
- The subject requires alternative (rescue) antibacterial treatment for CABP prior to the Early Clinical Response assessment related to either (a) progression or development of new symptoms attributable to CABP or (b) development of infectious complications of CABP (eg, empyema, lung abscess).

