5 STUDY DESIGN CONSIDERATIONS

5.1 Study Design

This is a randomized (1:1), double-blind, active comparator-controlled, Phase 3 study comparing 7 to 14 days of treatment with either omadacycline or moxifloxacin for the treatment of adults with CABP. The number of subjects in Pneumonia Outcomes Research Team (PORT) Risk Class II will be limited to no more than 15% of randomized subjects. Subject randomization will be stratified across treatment groups by PORT Risk Class (II and III/IV), receipt of an allowed antibacterial therapy in the 72 hours prior to study treatment (yes and no) and geographic region (Western Europe/North America, Eastern Europe, and Rest of World). All subjects are expected to present with CABP severe enough to require a minimum of at least 3 days of intravenous (iv) treatment. After a minimum of 3 days of iv treatment, the investigator can switch the subject to oral (po) treatment if the subject is considered clinically stable and meets the criteria for transition to a po regimen.

Screening assessments will be performed within 24 hours before the first infusion of test article. The day of the first infusion of test article is defined as Day 1 and the day prior is Day-1; there is no Day 0. The study will have the following protocol-defined evaluations:

- Visits will be conducted daily on Days 1 through 7. The Day 6 visit is optional for subjects that have been switched to po test article and have been discharged from a hospital setting. A Day 10 visit should be conducted for subjects with treatment extending beyond 9 days, unless this visit coincides with the End of Treatment (EOT) Visit.
- EOT Visit: to be performed on the calendar day of, or within 2 days following the last dose of any test article. If a subject withdraws prematurely or terminates participation in the study before completion, the EOT Visit should be conducted.
- PTE Visit: to be performed 5 to 10 days after the subject's last day of study therapy
- Final Follow-up assessment: Study Day 30-37 (after start of first infusion of test article)

A detailed Schedule of Study Procedures is provided in [Appendix 1](#).

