8.3 Handling of Missing Data

Missing data will be handled as outlined below:

- All missing and partial dates for adverse events or for medications received after randomization will be queried for a value. If no value can be obtained, substitutions will be made as detailed in [Appendix 3](#). These substitutions will be used in calculations; however, the actual value recorded on the eCRF will be used in all listings.
- Missing start and stop times for prior and concomitant antibiotics will be queried for a value. If no value can be obtained but the site indicates the antibiotic was received (onset time) prior to the first dose of test article, 00:01 will be used for the onset time. If the site also indicates that the end time was prior to the first dose of test article, 00:01 will be used for end time. The actual value (blank) will be recorded on the eCRF and will be used in the listings.
- Missing times for assessments of CABP symptoms will be queried for a value. If minutes are not available, the time will be recorded to the closest hour.
- If no value can be obtained for all other times for events and assessments occurring after randomization, the time will not be imputed but will remain missing.
- The severity and causality assessment for adverse events cannot be missing. Missing data will be queried for a value.

For clinical and microbiological response, missing data will be handled as follows:

- For the primary outcome measure (Early Clinical Response at 72 to 120 hours after administration of the first dose of test article):
 - The subject will be considered to have missing data if an assessment of all of the CABP symptoms (cough, sputum production, pleuritic chest pain, and dyspnea) is not made from 72 to 120 hours after the administration of the first dose of test article, unless the subject is considered a Clinical Failure for another reason. Subjects who do not have at least 2 symptoms of CABP at baseline will also be considered to have missing data unless the subject is considered a Clinical Failure for another reason. Subjects with missing data will be defined as an Indeterminate response which is essentially a Clinical Failure for the primary analysis in the ITT population.

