 - If the time of administration of the first dose of test article is missing, the subject will be defined as an Indeterminate response (unless the subject is considered a Clinical Failure for another reason) which is essentially a Clinical Failure for the primary analysis in the ITT population.
- For the secondary outcome measures (investigator's assessment of Clinical Response at the EOT and PTE Visits):
 - Subjects will be defined as an Indeterminate if the investigator cannot determine whether the subject is a Clinical Success or Failure at the EOT or PTE Visits or the subject has a missing response (see [Table 1](#)). By definition, subjects with an Indeterminate response are included in the denominator for analyses in the ITT and

microITT populations, and thus, are considered Clinical Failures. Subjects with an Indeterminate response are excluded from the CE-EOT, CE-PTE, ME-EOT and ME-PTE populations.

- For microbiologic response:
 - If no post-baseline source specimen is obtained and the subject has an investigator’s assessment of Clinical Response, the per-pathogen microbiological response is based on the investigator’s assessment of Clinical Response (ie, the response is a presumed response). A per-pathogen microbiological response at the EOT Visit or PTE Visit will be considered Indeterminate only if the Clinical Response at EOT or PTE is also Indeterminate.
- Missing values for other individual data points will remain as missing. Missing values will not be imputed and only observed values will be used in data analyses and presentations.
- Where individual data points are missing, categorical data will be summarized based on reduced denominators (ie, only subjects with available data will be included in the denominators).

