8.6 Visit Windows/Unscheduled Visits

For the primary efficacy outcome, if more than one complete assessment of the symptoms of CABP is done in the Early Clinical Assessment window of 72 to 120 hours after administration of the first dose of test article, the latest will be used. For secondary and additional efficacy outcomes, the data collected at the EOT and PTE Visits, regardless of when these occur will be utilized in the ITT and microITT analyses. The CE and ME populations exclude subjects with a visit occurring outside the window allowed per protocol.

For each safety outcome, analyses will utilize assessments occurring during the scheduled visit windows (provided in [Table 7](#)). Thus, if a subject has a visit outside the scheduled visit window, for example, a PTE Visit occurred 20 days after the subject's last day of therapy, the assessment will not be summarized with the PTE Visit but will be considered an unscheduled assessment. If a subject does not have an assessment at a scheduled visit and an unscheduled assessment was taken within the window for the time point (for example, 5 to 10 days after the subject's last day of therapy for PTE), these assessments will be summarized in the by time point analyses. If more than one measurement is taken during the visit window, the value taken on the scheduled visit will be utilized or if no scheduled visit was done, the first (earliest) measurement in the visit window will be used. If more than one measurement is taken on the same day, the assessment closest to the start of the dose will be used for on treatment values and the last measurement on the day will be used for post-treatment values. For worst overall post-baseline analyses, all assessments including those obtained from unscheduled visits will be included.

Table 7. Scheduled Study Visits

Study Visit	Study Day	Notes
Baseline	Day -1 or Day 1	Except where indicated, last measurement prior to the first dose of test article. Screening assessments are to be taken within 24 hours prior to the first dose of test article. If no test article is taken, the date and time of randomization is used in place of the first dose of test article.
On Treatment	Day 1-Day 10	Day 6 visit is optional for subjects that have been switched to po test article and have been discharged from a hospital setting. A Day 10 visit will be conducted for subjects with treatment extending beyond 9 days, unless this visit coincides with the EOT Visit.

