EOT		Within 2 days following the last dose of test article
PTE		5-10 days after the subject's last day of therapy
Final Follow-up	Day 30-37	30-37 days after the start of the first infusion of test article

Study Day is calculated relative to the first dose of test article (Day 1); there is no Day 0 – the day prior to the first dose of test article is Day -1. If no test article is taken, Study Day is calculated relative to the date of randomization.

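### A missing first-dose clock time makes Early Clinical Response Indeterminate even when the dates alone place a Day 5 symptom assessment inside 72 to 120 hours

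*Combined protocol and SAP*

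**What the plan says.** SAP section 8.3 has a specific rule for the primary outcome: "If the time of administration of the first dose of test article is missing, the subject will be defined as an Indeterminate response". The only exception is a subject who is a Clinical Failure for another reason. The section adds that the resulting Indeterminate is in effect a failure in the ITT primary analysis.

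The same section treats the outcome as missing when a full symptom assessment "is not made from 72 to 120 hours after the administration of the first dose of test article".

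The calendar is fixed elsewhere. SAP section 5.1: "The day of the first infusion of test article is defined as Day 1". The note to SAP Table 7 in section 8.6: "Study Day is calculated relative to the first dose of test article (Day 1); there is no Day 0".

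The protocol (version 2.0) schedules daily visits on Days 1 to 7 in section 14.1. Day 6 is optional only for subjects switched to oral treatment and discharged. For those discharged before Day 6, protocol section 17.2.3.1 says that "visits must be conducted on study Days 4 and 5, while a study Day 6 visit is optional".

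SAP section 8.6 decides between several assessments: "if more than one complete assessment of the symptoms of CABP is done in the Early Clinical Assessment window of 72 to 120 hours", the latest one is used.

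**The concern.** SAP section 5.2.1 reserves Indeterminate for data so incomplete that the response cannot be worked out. Protocol section 22.15 ties it to a missing field that is needed for the determination. The dose-time rule in SAP section 8.3 goes further than either. It fires whenever the clock time is absent, whether or not that time is needed.

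Where it is not needed, an observed response is set aside. The exception for subjects already failing means that the rule only ever turns would-be successes into counted failures. A clerical gap then lowers the success rate in the primary analysis.

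The SAP is less strict elsewhere. For prior and concomitant antibiotics, section 8.3 fills in a missing time when the order relative to the first dose is known. For adverse events, section 11.1 classifies by date when the time is missing. The primary endpoint has no comparable provision for the dose time.

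**Working it through.** **1. Where does each study day fall?** Inputs: Day 1 is the date of the first infusion and there is no Day 0 (SAP sections 5.1 and 8.6), so Day D is the dose date plus D − 1 days. Let the dose be at clock hour h and the assessment at clock hour a, both at least 0 and below 24. Then

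elapsed hours = 24 × (D − 1) + a − h, where a − h lies strictly between −24 and +24.

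Enumerating all 1440 × 1440 pairs of clock minutes gives:

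| Study day | Shortest | Longest | Share of pairs in 72–120 h |
|---|---|---|---|
| 3 | 24 h 01 min | 71 h 59 min | 0% |
| 4 | 48 h 01 min | 95 h 59 min | about 50% |
| 5 | 72 h 01 min | 119 h 59 min | 100% |
| 6 | 96 h 01 min | 143 h 59 min | about 50% |
| 7 | 120 h 01 min | 167 h 59 min | 0% |

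Day 5 is the only day that is certain to be inside. A daylight-saving change could move the extreme cases by 1 hour.

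**2. Which assessment counts?** SAP section 8.6 takes the latest complete one in the window.
- Day 4 can never displace a complete Day 5 assessment, because it is earlier.
- Day 7 is never in the window.
- Day 6 may or may not be.

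So with the dose time missing, dates alone settle the response in two cases: there is no complete Day 6 assessment, or Day 6 gives the same response as Day 5. If the two differ, dates do not settle it.

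**3. The plan's own power figure.** Inputs from SAP section 5.1.1: 750 subjects (375 per arm), 79% in both arms, margin 0.10, one-sided alpha 0.025, stated power 92%. The Farrington-Manning formula is

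power = Φ[(0.10 − 1.96 × s0) / s1].

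- The rates restricted to a difference of −0.10 are 0.8316 and 0.7316, so s0 = √[(0.8316 × 0.1684 + 0.7316 × 0.2684) / 375] = 0.02995.
- s1 = √[2 × 0.79 × 0.21 / 375] = 0.02975.
- (0.10 − 0.05870) / 0.02975 = 1.388, and Φ(1.388) = 0.917.

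The unpooled normal approximation gives 92.0%. The stated figure is reproduced.

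**4. Size of the effect.** The documents give no rate of missing dose times, so the share x is an assumption. Suppose it is equal in both arms, unrelated to outcome, and every affected success is lost. The success rate becomes 0.79 × (1 − x).

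| x | Subjects (750x) | Success rate | Power |
|---|---|---|---|
| 0 | 0 | 79.0% | 91.7% |
| 0.2% | 1.5 | 78.8% | 91.6% |
| 0.5% | 3.75 | 78.6% | 91.4% |
| 1% | 7.5 | 78.2% | 91.1% |
| 2% | 15 | 77.4% | 90.4% |

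**The case against.** **The trigger should hardly ever occur.** The first dose is an in-hospital infusion whose start and stop times must go into source and eCRF (protocol section 14.3.1.1). Vital signs, ECGs and later doses are timed from it, and all queries must be resolved before lock (section 25.3). This stands, and it is why the point is minor.

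**The damage is bounded.** SAP section 10.2 plans a sensitivity analysis that counts subjects with missing data as successes, so any influence on the conclusion would show. That is true as far as it goes. But the primary analysis makes these subjects failures and the sensitivity analysis makes them successes, and neither uses the Day 5 result.

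**Day 5 does not always decide.** A reader might infer that a missing dose time can never affect window membership. The documents do not support this. Inpatients are due a Day 6 visit, a Day 6 assessment may still be inside 120 hours, and section 8.6 would then prefer it. This objection stands in full and limits both the point and the remedy.

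**Missing symptom-assessment times are a different matter.** A reader might extend the point to these, citing the sentence in SAP section 8.3 that "the time will not be imputed but will remain missing". That sentence covers all other times. CABP symptom times have their own bullet: they are queried, and recorded to the closest hour if minutes are unavailable. Nothing there says that an untimed symptom assessment makes the subject Indeterminate. The point is therefore confined to the first-dose time.

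**Conclusion.** The point holds in a narrow form. When the first-dose date is known, its time is not, and a complete Day 5 assessment exists without a conflicting Day 6 assessment, the response can be determined. SAP section 8.3 nevertheless scores the subject as a failure unless already failing for another reason. That goes beyond the SAP's own reason for using Indeterminate.

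The number affected is not in the documents and is likely very small. Under the assumed range of 0.2% to 2% in both arms, power falls from about 91.7% to between 91.6% and 90.4%. This is an upper figure for each assumed rate, because it treats every affected success as recoverable from Day 5.

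A reader might infer that the rule threatens the trial's power. That would need the missing times to fall in one arm: at 2% of omadacycline subjects only, power would be 79.6%. Nothing in the documents points to such an imbalance. The infusion schedule and the time recording are the same in both arms, and the trial is double-blind.

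**What to change.** Replace the dose-time rule in SAP section 8.3 with:

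> If the first-dose time cannot be obtained but its date is known, the latest complete symptom assessment dated Study Day 5 is treated as within 72–120 h and used to derive Early Clinical Response, provided that no complete Day 6 assessment exists or that the Day 6 assessment gives the same response; otherwise the subject is Indeterminate (unless a Clinical Failure for another reason).

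Study Day here should mean the date of the assessment counted from the first-dose date, not the visit label.

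The cost is one extra derivation rule. It may use Day 5 where the latest-in-window rule of section 8.6 would have picked Day 6, but only when the two give the same response, so it cannot change the result. It should be adopted blinded, before database lock.

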8.4 Interim Analysis

An interim analysis to assess efficacy is not planned. However, a Data and Safety Monitoring Committee (DSMC) will review safety data (eg, AEs and SAEs, laboratory data, ECG assessments) by unblinded (treatment A and treatment B) treatment assignment on approximately a quarterly basis. However the DSMC can convene unscheduled meetings as necessary. A detailed DSMC charter outlines the responsibilities of the DSMC, format and frequency of the meetings, methods of providing data to and from the DSMC, statistical issues, documentation of the meeting outcomes, and communication pathways.

8.5 Pooling Strategy for Study Sites

Data will be pooled across site and geographic region (Western Europe/North America, Eastern Europe, Rest of World). Due to the large number of sites and the small number of subjects per site, no analyses by site will be conducted. Analyses by geographic region will be conducted as well as an adjusted analysis including geographic region as a stratification factor.

8.6 Visit Windows/Unscheduled Visits

For the primary efficacy outcome, if more than one complete assessment of the symptoms of CABP is done in the Early Clinical Assessment window of 72 to 120 hours after administration of the first dose of test article, the latest will be used. For secondary and additional efficacy outcomes, the data collected at the EOT and PTE Visits, regardless of when these occur will be utilized in the ITT and microITT analyses. The CE and ME populations exclude subjects with a visit occurring outside the window allowed per protocol.

For each safety outcome, analyses will utilize assessments occurring during the scheduled visit windows (provided in [Table 7](#)). Thus, if a subject has a visit outside the scheduled visit window, for example, a PTE Visit occurred 20 days after the subject's last day of therapy, the assessment will not be summarized with the PTE Visit but will be considered an unscheduled assessment. If a subject does not have an assessment at a scheduled visit and an unscheduled assessment was taken within the window for the time point (for example, 5 to 10 days after the subject's last day of therapy for PTE), these assessments will be summarized in the by time point analyses. If more than one measurement is taken during the visit window, the value taken on the scheduled visit will be utilized or if no scheduled visit was done, the first (earliest) measurement in the visit window will be used. If more than one measurement is taken on the same day, the assessment closest to the start of the dose will be used for on treatment values and the last measurement on the day will be used for post-treatment values. For worst overall post-baseline analyses, all assessments including those obtained from unscheduled visits will be included.

Table 7. Scheduled Study Visits

Study Visit	Study Day	Notes
Baseline	Day -1 or Day 1	Except where indicated, last measurement prior to the first dose of test article. Screening assessments are to be taken within 24 hours prior to the first dose of test article. If no test article is taken, the date and time of randomization is used in place of the first dose of test article.
On Treatment	Day 1-Day 10	Day 6 visit is optional for subjects that have been switched to po test article and have been discharged from a hospital setting. A Day 10 visit will be conducted for subjects with treatment extending beyond 9 days, unless this visit coincides with the EOT Visit.
EOT		Within 2 days following the last dose of test article
PTE		5-10 days after the subject's last day of therapy
Final Follow-up	Day 30-37	30-37 days after the start of the first infusion of test article

Study Day is calculated relative to the first dose of test article (Day 1); there is no Day 0 – the day prior to the first dose of test article is Day -1. If no test article is taken, Study Day is calculated relative to the date of randomization.

9 STATISTICAL ANALYSIS METHODS

9.1 Subject Disposition

The number of Screen Failures and reason for screen failure will be presented overall and by geographic region (Western Europe/North America, Eastern Europe, Rest of World). A listing, grouped by randomization stratum (PORT Risk Class, receipt of prior antibiotics, and geographic region), will be provided that indicates the subject's date and time of randomization, randomized treatment assignment, randomization number, and block number.

The number of subjects included in each of the analysis populations (ie, ITT, Safety, microITT, expanded microITT, CE-EOT, CE-PTE, ME-EOT, and ME-PTE) will be summarized by treatment group, and geographic region and country. A table will summarize the reasons for exclusion from each population and a listing will be provided that indicates each subject's inclusion in/exclusion from the populations and the reason for exclusion from each of the populations.

A listing will be provided of randomized subjects who did not meet all inclusion/exclusion criteria, and which criteria were not met. The number and percentage of subjects completing the study (defined as receiving at least 1 dose of test article and returning for all of the EOT, PTE, and Follow-up Visits), not completing the study, missing each of the EOT and PTE Visits, and prematurely discontinuing from test article will be presented for each treatment group and overall for the ITT, microITT, and CE-PTE populations (by definition, a subject in the CE-PTE population cannot have missed the PTE Visit, unless the subject was a clinical failure at the EOT Visit). Reasons for premature discontinuation of test article, not completing the study, and for missing each of the visits, as recorded on the eCRF will be summarized (number and percentage) by treatment group for the ITT, microITT, and CE-PTE populations. Percentages of subjects discontinued from test article and not completing the study will be compared between treatment groups using Fisher's exact test. A listing of all subjects who prematurely discontinued from test article or not completing the study will be presented, and the primary reason for discontinuation of test article or not completing the study, as well as the visit(s) missed and the reason for missing the visit(s), will be provided.

